6.1 Anticipated Toxicities

6.1.1 Biopsy

Prostate biopsies are generally well-tolerated outpatient procedures. In addition to anticipatory anxiety, participants are at risk of the following complications:

Common (occurring in 20 to 90 out of 100 participants)

- mild discomfort (44%)
- hematuria (66%)
- hematospermia (93%)
- hematochezia (37%)
- fever (20%)

Occasional (occurring in 1 or 2 our of 100 participants)

- persistent bleeding (1-2%)
- urinary retention (<1%)
- infection requiring hospitalization (1-2%)

6.1.2 MRI

Participants may experience frustration or anxiety related to the time spent obtaining the MRI. Participants will also be at risk of the typical reactions from MRI with gadolinium contrast administration:

Occasional (occurring 2 or 3 out of 100 participants)

 Mild nausea (with or without vomiting), tingling sensation, headache, dizziness, coldness at the injection site, headache, warmth or pain at the injection site, paresthesias, dizziness and itching.

Rare (occurring in 1 participant or less out of 100)

- Severe anaphylactic reaction
- Severe nephrogenic systemic fibrosis (NSF) in participants with chronic renal insufficiency

7. STUDY CALENDAR

	Pre- Study	MRI Visit (2-14 months post initial biopsy)	Final Bx visit (within 3 months of MRI visit)	End of Study Visit (within 60 days of final bx)
Informed consent	X			
History ^a	X			
Pathology review	X ^b		X ^d	
PSA	X ^c			Xe
Concurrent meds	X			
Height and weight	X			
Performance Status	X			
Patient-reported health	X^{f}			X
Adverse event evaluation		X	X	X

- a: biopsy date, clinical T-category, was the subject staged with a CT of the abdomen and pelvis; was the subject staged with a bone scan; ACE-27 Comorbidity index (Appendix E)
- b: DF/HCC pathology review of original biopsy (no. cores taken, no. cores positive for cancer; % involvement for each positive core; Gleason grade for each positive core; presence and grade of tertiary Gleason grade; evidence of extracapsular extension; evidence of perineural invasion)
- c: last PSA level prior to biopsy diagnosing the prostate cancer
- d: DF/HCC pathology review of "random" and targeted biopsy (as needed) (no. cores taken, no. cores positive for cancer; % involvement for each positive core; Gleason grade for each positive core; presence and grade of tertiary Gleason grade; evidence of extracapsular extension; evidence of perineural invasion)
- e: most recent PSA value
- f: MUIS-AS, Appendix A; SSS-Ca, Appendix B; EPIC-CP, Appendix C; AUA SI, Appendix D

8. ADVERSE EVENT REPORTING REQUIREMENTS

8.1 Definitions

8.1.1 Adverse Event (AE)

An adverse event (AE) is any undesirable sign, symptom or medical condition or experience that develops or worsens in severity after starting the first dose of study treatment or any procedure specified in the protocol, even if the event is not considered to be related to the study.

Abnormal laboratory values or diagnostic test results constitute adverse events only if they induce clinical signs or symptoms or require treatment or further diagnostic tests.

8.1.2 Serious adverse event (SAE)

A serious adverse event (SAE) is any adverse event, occurring at any dose and regardless of causality that:

- Results in death
- Is life-threatening. Life-threatening means that the person was at immediate risk of death from the reaction as it occurred, i.e., it does not include a reaction which hypothetically might have caused death had it occurred in a more severe form.
- Requires or prolongs inpatient hospitalization (i.e., the event required at least a 24-hour hospitalization or prolonged a hospitalization beyond the expected length of stay). Hospitalization admissions and/or surgical operations scheduled to occur during the study period, but planned prior to study entry are not considered SAEs if the illness or disease existed before the person was enrolled in the trial, provided that it did not deteriorate in an unexpected manner during the trial (e.g., surgery performed earlier than planned).
- Results in persistent or significant disability/incapacity. Disability is defined as a substantial disruption of a person's ability to conduct normal life functions.
- Is a congenital anomaly or birth defect; or
- Is an important medical event when, based upon appropriate medical judgment, it may jeopardize the participant and require medical or surgical intervention to prevent one of the outcomes listed above. Examples of such medical events include allergic bronchospasm requiring intensive treatment in an emergency room or at home; blood dyscrasias or convulsions that do not result in inpatient hospitalization, or the development of drug dependency or drug abuse.

Events **not** considered to be serious adverse events are hospitalizations for:

- routine treatment or monitoring of the studied indication, not associated with any deterioration in condition, or for elective procedures
- elective or pre-planned treatment for a pre-existing condition that did not worsen
- emergency outpatient treatment for an event not fulfilling the serious criteria outlined above and not resulting in inpatient admission

• respite care

8.1.3 Expectedness

Adverse events can be 'Expected' or 'Unexpected.'

8.1.3.1 Expected adverse event

Expected adverse events are those that have been previously identified as resulting from administration of the agent. For the purposes of this study, an adverse event is considered expected when it appears in the current adverse event list, the Investigator's Brochure, the package insert or is included in the informed consent document as a potential risk.

Refer to Section 6.1 for a listing of expected adverse events associated with the study agent(s).

8.1.3.2 Unexpected adverse event

For the purposes of this study, an adverse event is considered unexpected when it varies in nature, intensity or frequency from information provided in the current adverse event list, the Investigator's Brochure, the package insert or when it is not included in the informed consent document as a potential risk.

8.1.4 Attribution

Attribution is the relationship between an adverse event or serious adverse event and the study treatment. Attribution will be assigned as follows:

- Definite The AE is clearly related to the study treatment.
- Probable The AE is likely related to the study treatment.
- Possible The AE may be related to the study treatment.
- Unlikely The AE is doubtfully related to the study treatment.
- Unrelated The AE is clearly NOT related to the study treatment.

8.2 Procedures for AE and SAE Recording and Reporting

Participating investigators will assess the occurrence of AEs and SAEs at all participant evaluation time points during the study.

All AEs and SAEs whether reported by the participant, discovered during questioning, directly observed, or detected by physical examination, laboratory test or other means, will be recorded in the participant's medical record and on the appropriate study-specific case report forms.

The descriptions and grading scales found in the revised NCI Common Terminology Criteria for Adverse Events (CTCAE) version 4.0 will be utilized for AE reporting. All appropriate treatment areas should have access to a copy of the CTCAE version 4.0.

A copy of the CTCAE version 4.0 can be downloaded from the CTEP website at:

http://ctep.cancer.gov/protocolDevelopment/electronic_applications/ctc.htm.

8.3 Reporting to the Study Sponsor

8.3.1 Serious Adverse Event Reporting

All serious adverse events that occur after the initial study procedure, or within 30 days of the last study procedure treatment must be reported to the DF/HCC Overall Principal Investigator on the local institutional SAE form. This includes events meeting the criteria outlined in Section 11.1.2, as well as the following:

- Grade 2 (moderate) and Grade 3 (severe) Events Only events that are unexpected and possibly, probably or definitely related/associated with the intervention.
- All Grade 4 (life-threatening or disabling) Events Unless expected AND specifically listed in the protocol as not requiring reporting.
- All Grade 5 (fatal) Events When the participant is enrolled and actively participating in the trial OR when the event occurs within 30 days of the last study intervention.

Note: If the participant is in long term follow up, report the death at the time of continuing review.

Participating investigators must report each serious adverse event to the DF/HCC Overall Principal Investigator within 24 business hours of learning of the occurrence. In the event that the participating investigator does not become aware of the serious adverse event immediately (e.g., participant sought treatment elsewhere), the participating investigator is to report the event within 24 business hours after learning of it and document the time of his or her first awareness of the adverse event. Report serious adverse events by telephone, email or facsimile to:

Within the following 24-48 business hours, the participating investigator must provide follow-up information on the serious adverse event. Follow-up information should describe whether the event has resolved or continues, if and how the event was treated, and whether the participant will continue or discontinue study participation.

8.3.2 Non-Serious Adverse Event Reporting

Non-serious adverse events will be reported to the DF/HCC Overall Principal Investigator on the toxicity Case Report Forms.

8.4 Reporting to the Institutional Review Board (IRB)

Investigative sites within DF/HCC will report all serious adverse events directly to the DFCI Office for Human Research Studies (OHRS).

Other investigative sites should report serious adverse events to their respective IRB according to the local IRB's policies and procedures in reporting adverse events. A copy of the submitted institutional SAE form should be forwarded to:

The DF/HCC Principal Investigator will submit SAE reports from outside institutions to the DFCI Office for Human Research Studies (OHRS) according to DFCI IRB policies and procedures in reporting adverse events.

8.5 Reporting to Hospital Risk Management

Participating investigators will report to their local Risk Management office any subject safety reports or sentinel events that require reporting according to institutional policy.

8.6 Monitoring of Adverse Events and Period of Observation

All adverse events, both serious and non-serious, and deaths that are encountered from initiation of study intervention, throughout the study, and within 30 days of the last study intervention should be followed to their resolution, or until the participating investigator assesses them as stable, or the participating investigator determines the event to be irreversible, or the participant is lost to follow-up. The presence and resolution of AEs and SAEs (with dates) should be documented on the appropriate case report form and recorded in the participant's medical record to facilitate source data verification.

For some SAEs, the study sponsor or designee may follow-up by telephone, fax, and/or monitoring visit to obtain additional case details deemed necessary to appropriately evaluate the SAE report (e.g., hospital discharge summary, consultant report, or autopsy report).

Participants should be instructed to report any serious post-study event(s) that might reasonably be related to participation in this study. Participating investigators should notify the DF/HCC Overall Principal Investigator and their respective IRB of any unanticipated death or adverse event occurring after a participant has discontinued or terminated study participation that may reasonably be related to the study.

9. DATA AND SAFETY MONITORING

9.1 Data Reporting

9.1.1 Method

The QACT will collect, manage, and monitor data for this study.

9.1.2 Data Submission

The schedule for completion and submission of case report forms (paper or electronic) to the QACT is as follows:

Form	Submission Timeline
Eligibility Checklist	Complete prior to registration with QACT
On Study Form	Within 14 days of registration
Baseline Assessment Form	Within 14 days of registration
Treatment Form	Within 10 days of the last day of the cycle
Adverse Event Report Form	Within 10 days of the last day of the cycle
Response Assessment Form	Within 10 days of the completion of the cycle required for response evaluation
Off Treatment/Off Study Form	Within 14 days of completing treatment or being taken off study for any reason
Follow up/Survival Form	Within 14 days of the protocol defined follow up visit date or call

9.2 Safety Meetings

The DF/HCC Data and Safety Monitoring Committee (DSMC) will review and monitor toxicity and accrual data from this trial. The committee is composed of clinical specialists with experience in oncology and who have no direct relationship with the study. Information that raises any questions about participant safety will be addressed with the Principal Investigator and study team.

The DSMC will meet quarterly and/or more often if required to review toxicity and accrual data. Information to be provided to the committee may include: up-to-date participant accrual; current dose level information; DLT information; all grade 2 or higher unexpected adverse events that have been reported; summary of all deaths occurring within 30 days for Phase I or II protocols; for gene transfer protocols, summary of all deaths while being treated and during active follow-up; any response information; audit results, and a summary provided by the study team. Other information (e.g. scans, laboratory values) will be provided upon request.

9.3 Monitoring

Involvement in this study as a participating investigator implies acceptance of potential audits or inspections, including source data verification, by representatives designated by the DF/HCC Overall Principal Investigator (or Protocol Chair) or DF/HCC. The purpose of these audits or inspections is to examine study-related activities and documents to determine whether these activities were conducted and data were recorded, analyzed, and accurately reported in accordance with the

protocol, institutional policy, Good Clinical Practice (GCP), and any applicable regulatory requirements.

All data will be monitored for timeliness of submission, completeness, and adherence to protocol requirements. Monitoring will begin at the time of participant registration and will continue during protocol performance and completion.

10. REGULATORY CONSIDERATIONS

10.1 Protocol Review and Amendments

This protocol, the proposed informed consent and all forms of participant information related to the study (e.g., advertisements used to recruit participants) and any other necessary documents must be submitted, reviewed and approved by a properly constituted IRB governing each study location.

Any changes made to the protocol must be submitted as amendments and must be approved by the IRB prior to implementation. Any changes in study conduct must be reported to the IRB. The DF/HCC Overall Principal Investigator (or Protocol Chair) will disseminate protocol amendment information to all participating investigators.

All decisions of the IRB concerning the conduct of the study must be made in writing.

10.2 Informed Consent

All participants must be provided a consent form describing this study and providing sufficient information for participants to make an informed decision about their participation in this study. The formal consent of a participant, using the IRB approved consent form, must be obtained before the participant is involved in any study-related procedure. The consent form must be signed and dated by the participant or the participant's legally authorized representative, and by the person obtaining the consent. The participant must be given a copy of the signed and dated consent document. The original signed copy of the consent document must be retained in the medical record or research file.

10.3 Ethics and Good Research Practice

This study is to be conducted according to the following considerations, which represent good and sound research practice:

- US Code of Federal Regulations (CFR) governing clinical study conduct and ethical principles that have their origin in the Declaration of Helsinki
 - o Title 21 Part 50 Protection of Human Subjects www.access.gpo.gov/nara/cfr/waisidx 02/21cfr50 02.html

- Title 21 Part 54 Financial Disclosure by Clinical Investigators www.access.gpo.gov/nara/cfr/waisidx 02/21cfr54 02.html
- Title 21 Part 56 Institutional Review Boards www.access.gpo.gov/nara/cfr/waisidx 02/21cfr56 02.html
- o Title 21 Part 312 Investigational New Drug Application www.access.gpo.gov/nara/cfr/waisidx 02/21cfr312 02.html
- State laws
- DF/HCC research policies and procedures http://www.dfhcc.harvard.edu/clinical-research-unit-cru/policies-and-procedures/

It is understood that deviations from the protocol should be avoided, except when necessary to eliminate an immediate hazard to a research participant. In such case, the deviation must be reported to the IRB according to the local reporting policy.

10.4 Study Documentation

The investigator must prepare and maintain adequate and accurate case histories designed to record all observations and other data pertinent to the study for each research participant. This information enables the study to be fully documented and the study data to be subsequently verified.

Original source documents supporting entries in the case report forms include but are not limited to hospital records, clinical charts, laboratory and pharmacy records, recorded data from automated instruments, microfiches, photographic negatives, microfilm or magnetic media, and/or x-rays.

10.5 Records Retention

All study-related documents must be retained for the maximum period required by applicable federal regulations and guidelines or institutional policies.

11. STATISTICAL CONSIDERATIONS

11.1 Study Design/Primary Objective

The primary objective is to determine the sensitivity and specificity of Mp-erMRI relative to repeated standard 12-core TRUS biopsy for classifying upgrading of disease extent or Gleason grade in men considering AS. We hypothesize MP-erMRI prior to AS for men with low risk disease can identify men who harbor more extensive or higher risk prostate cancer.

The study will plan to enroll 130 participants who had diagnostic biopsy less than one year prior to enrollment. After enrollment, participants will undergo a MP-erMRI. This will be reviewed and participants will be characterized into 3 groups: "not reclassified" characterized by findings consistent with small, low-Gleason grade organ-confined tumors, "reclassified" characterized by large, higher-Gleason grade organ-confined tumors, and radiographic T3 and or N1 disease. Less than 10% (roughly 10) of participants who belong to group 3 will be taken off study. Those in groups 1 and 2 will proceed within 3 months of the MP-erMRI to a standard 12-core TRUS biopsy.

11.2 Hypothesis assumptions:

Participants in groups 1 and 2 will receive 12 core TRUS re-biopsy within 3 months of undergoing MP-erMRI. TRUS re-biopsy will be assumed as the gold standard for determining tumor size and grade.

11.2.1 Null hypothesis:

	TRUS Re-biop		
MP-erMRI Results	No Disease Upgrade	Disease Upgrade	Total
Not Reclassified	72	9	81
Reclassified	18 (20%)	21 (70%)	39
Total	90	30	120

11.2.2 Alternative hypothesis:

	TRUS Re-biog		
MP-erMRI Results	No Disease Upgrade	Disease Upgrade	Total
Not Reclassified	85	3	88
Reclassified	5 (6%)	27 (90%)	32
Total	90	30	120

11.3 Power and sample size calculation:

A true positive fraction (TPF) is defined as the probability of MP-erMRI tests show disease re-classified results when participants truly have upgraded disease according to 12 core TRUS re-biopsies. A false positive fraction (FPF) is defined as the probably of MP-erMRI tests show re-classified disease results when no upgrade disease was observed on 12 core TRUS re-biopsies. A TPF (sensitivity) of 90% and FPF (1-specificity) of 6% would be considered promising, whereas a TPF of ≤70% and a FPF of ≥20% are unacceptable. Sample size is calculated using the formula with asymptotic variances as proposed by Pepe [71], followed by a set of 5000 simulation to assess that the power is adequate. Simulation was done using STATA scrsize package (http://labs.fhcrc.org/pepe/dabs/software.html). Results showed that with 120 participants (25% have upgrade

re-biopsy vs. biopsy prior to enrollment), 81% power can be achieved (1-sided alpha 0.1). This ensures that there is at least 80% chance of drawing a positive conclusion if the MP-MRI is 94% specific and 90% sensitive.

11.4 Primary Analysis:

The observed TPF and FPF will be summarized as percentages with 90% CI. Joint CIs for TPF and FPF will also be examined. A positive conclusion is drawn if the lower limit of TPF is above the minimally acceptable level of 70% and the upper limit of FPF is below the minimally acceptable level of 20%. Table below gives 80% confidence intervals for the true but unknown TPF and FPF, given possible observed participants with reclassified disease by MRI among 30 true reclassified and 90 non-reclassified cases (by re-biopsy). Table below is an example of 80% CI given different scenarios observed reclassified participants number.

Disease Upgra	ade by Re-bi	lopsy (n=30)	No Upgrade by Re-biopsy (N=90)		
Observed	Observed	80% CI	Observed	Observed	80% CI
reclassified	TPF		Reclassified	FPR	
N by MRI			N by MRI		
27	90%	(79%, 96%)	5	6%	(3%, 10%)
25	83%	(71%, 92%)	10	11%	(7%, 17%)
23	77%	(64%, 87%)	15	17%	(12%, 23%)
21	70%	(57%, 81%)	18	20%	(15%, 26%)

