More specifically, the group from Princess Margaret Hospital reported on a prospective AS protocol in which all men received multi-parametric MRI at the time of enrollment to assess its role in reclassifying their disease [58]. In this study, 60 men with T1c, Gleason 6, PSA <10 ng/mL, ≤3 cores involved and <50% involvement of any one core were enrolled. The 1.5 Tesla MRI was interpreted to classify men into three groups: (1) those with no visible tumor, (2) those with tumor ≤1 cm in size, and (3) those with tumor >1 cm (used to correspond to Epstein criterion for clinically significant disease). Those with either no tumor visible or with a tumor ≤1 cm in size were asked to undergo a repeat biopsy at approximately one year after initial diagnosis. Those with lesions larger than 1 cm were asked to undergo an immediate repeat biopsy using a TRUS approach targeting the area of interest [59]. Reclassification was defined as Gleason 7, more than 3 positive cores or more than 50% of any one core involved. The overall reclassification rate was 32%, with 77%, 25% and 9% in groups 3, 2, and 1 respectively. Groups 3 and 2 had a higher mean number of biopsies than group 1 (16.2, 15.3 and 12.3 respectively). Half of the reclassifications were for Gleason 7 disease on rebiopsy and this finding was significantly more common among those with larger MRI lesions.

Given differences in how the groups were treated in this study, more biopsies in those with larger lesions and targeted biopsies for those with larger lesions, we aim to further clarify the role of MP-MRI in reclassifying men considering AS. We will specifically evaluate the accuracy of MP-MRI relative to standard TRUS biopsy as that has remained the gold standard for disease classification in men followed on surveillance in the published literature. If MP-MRI could replace repeat biopsy for men considering AS, it could have a dramatic impact on successfully selecting men likely to safely remain on surveillance.

Patient-reported outcomes in active surveillance

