5.3.2 TRUS Biopsy Sampling

A 12-core biopsy will be performed without specific targeting of lesions noted at the time of MRI. This approach is intended to provide an unbiased assessment of the accuracy of MP-MRI in predicting men reclassified based on the current gold standard TRUS rebiopsy. Each core will be individually labeled with laterally and anatomic site within the prostate.

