5.3.3 Targeted rebiopsy

Participants in the **reclassified** category will have both a 12-core TRUS biopsy unguided by the results of the MRI and a biopsy targeting the lesion(s) of concern from the scan. The rationale for doing both biopsies is that to compare the MRI findings to the current goldstandard, a non-targeted TRUS biopsy, we need to include this regardless of the MRI findings. Because this biopsy may not capture the lesion noted on the scan, a targeted biopsy will be performed at the same time. The targeted biopsy will be performed according to the practices of the treating institution but will generally consist of conscious sedation with either an MRI-guided biopsy or a TRUS-guided biopsy directed based on images fused to the MRI. The number of cores taken will be at the discretion of the physician performing the biopsy. Standard of care transrectal ultrasound imaging (TRUS) may be augmented with the setup needed for spatial tracking of the TRUS images. The purpose of this is to facilitate research in spatial mapping biopsy samples within the prostate gland, and to aid with correlation of pathology analysis of the samples with TRUS and MRI imaging data. The tracking setup would be enabled by a tracking system consisting of an electromagnetic field transmitter that establishes the coordinate frame for tracking volume, and several sensors. The transmitter would be mounted on an articulated arm to the patient bed. One sensor will be attached to the handle of the TRUS probe before the procedure. The sensor will remain on the handle outside the patient at all times. The second sensor will be attached with the medical tape to the back of the patient. Prior to TRUS imaging, a calibration procedure may be necessary. If needed, such procedure would involve placing the TRUS probe in a water bath and imaging of a phantom, prior to the patient procedure. This component of the biopsy is not anticipated to add any additional risk or toxicity to the protocol.

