5.3.4 Pathologic assessment

- 5.3.4.1 All specimens will be formalin fixed and paraffin embedded as per usual clinical care. Pathology will be reviewed by a pathologist with GU expertise for Gleason grade, disease extent, and number of cores positive. Additional features such as perineural invasion and high-grade PIN will be noted though these will not be used to determine continued protocol eligibility. Each of the cores will be labeled for biopsy location at the time of procedure and will be individually reported. Pathology will be reviewed at the treating center. Specimens will also be labeled as to whether they came from the TRUS biopsy or the targeted biopsy
- 5.3.4.2 TRUS Biopsy: Participants will come off study if they no longer meet eligibility criteria following rebiopsy:
 - >3 cores positive for cancer
 - >50% of any single core containing cancer
 - any Gleason >3+3

- 5.3.4.3 Targeted Biopsy: Participants will be considered pathologically reclassified if either of the following criteria are met on the targeted biopsy:
 - Gleason >3+3
 - >7mm of any core involved with cancer

In this situation, using the criteria of number of cores involved with cancer will no longer be comparable across participants as the number of cores sampled will be variable based on the situation.

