11.6 Secondary Analysis

Secondary analysis will be summarized descriptively. Number and percentage of participants with reclassified disease by MP-erMRI will be summarized as numbers and percentages with 90% CI. Participants will be asked to complete self-reported health state questionnaires at enrollment and following the final on-protocol biopsy. A score will be given for each questionnaire answered by participants. The scores for the questionnaires will be summarized as median and inter-quartile ranges. Descriptive statistics will be utilized to correlate the targeted biopsy findings (disease extent in mm and Gleason score) with the findings from the MP-erMRI.

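### Does section 11.6 need to split targeted-biopsy results by TRUS result so that MRI false positives can be interpreted?

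*Combined protocol and SAP*

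**What the plan says.** Section 11.3 defines the false positive fraction (FPF) against the untargeted 12-core biopsy alone: "MP-erMRI tests show re-classified disease results when no upgrade disease was observed on 12 core TRUS re-biopsies". Section 11.2 takes TRUS re-biopsy as the gold standard. Section 5.3.2 gives the reason: leaving MRI lesions untargeted is "intended to provide an unbiased assessment of the accuracy of MP-MRI in predicting men reclassified".

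Section 5.3.3 adds targeted cores for every MRI-reclassified man: "Because this biopsy may not capture the lesion noted on the scan, a targeted biopsy will be performed at the same time". Section 5.3.4.3 supplies a separate outcome for those cores: "Participants will be considered pathologically reclassified if either of the following criteria are met on the targeted biopsy", namely Gleason >3+3 or ">7mm of any core involved with cancer". Section 5.3.4.1 keeps the two sources apart: "Specimens will also be labeled as to whether they came from the TRUS biopsy or the targeted biopsy".

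The planned analysis of the targeted cores is in section 11.6: "Descriptive statistics will be utilized to correlate the targeted biopsy findings (disease extent in mm and Gleason score) with the findings from the MP-erMRI". This answers the third secondary objective in sections 1.3 and 11.5. Neither place mentions the TRUS result.

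**The concern.** The protocol accepts that the reference biopsy can miss the lesion seen on MRI, and it collects the cores that would show this. Yet a man pathologically reclassified under section 5.3.4.3 can still be an MRI false positive under section 11.3, and no listed table counts such men. If the FPF criterion failed narrowly, readers would ask how many false positives were MRI over-calls and how many were lesions TRUS did not sample. A split produced only after a failure could look like a rescue. The criterion is also sharp: with 90 men not upgraded and 90% limits, one extra false positive can change the conclusion.

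**Working it through.** **Inputs.** 120 evaluable men, 30 upgraded and 90 not (sections 11.2 and 11.3). Promising values are TPF 90% and FPF 6%; unacceptable values are TPF 70% or lower and FPF 20% or higher (section 11.3). Success requires the TPF lower limit above 70% and the FPF upper limit below 20%. The section 11.4 text says 90% CI and its example table uses 80%; 90% exact (Clopper-Pearson) limits are used here unless stated.

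**1. The plan's own figure.** The rule passes with at least 26/30 true positives (lower limit 72.0%; 25/30 gives 68.1%) and at most 11/90 false positives (upper limit 19.4%; 12/90 gives 20.7%). Power = P(X ≥ 26 | 30, 0.90) × P(Y ≤ 11 | 90, 0.06) = 0.8245 × 0.9925 = 0.818, against the stated 81%. The primary design reproduces.

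**2. What TRUS misses would do.** Let m be the number of true upgrades that TRUS misses among the 90 men. Suppose the MRI is 90% sensitive and 94% specific against the true state. Then false positives = Bin(m, 0.9) + Bin(90 − m, 0.06), and P(at most 11) is:

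| m | Expected false positives | Chance of meeting FPF criterion |
|---|---|---|
| 0 | 5.4 | 99% |
| 2 | 7.1 | 97% |
| 5 | 9.6 | 80% |
| 8 | 12.1 | 41% |

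If the MRI flags only half of the missed men, the chance at m = 8 is 84%.

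**3. Which m is plausible.** The documents give no miss rate for this biopsy. Subtracting the plan's 30 upgrades from two background figures in section 2.1 gives a range:
- The 60-man MRI cohort had 32% reclassified: 0.32 × 120 = 38.4, so m is about 8. But 19/60 has a 90% interval of 22% to 43%, which includes the plan's 25%. In that cohort only lesions over 1 cm had immediate targeted biopsy, and the other men were rebiopsied at about one year, so the excess need not be TRUS misses.
- The immediate 14-core rebiopsy series had 27% upgraded or upstaged: 0.27 × 120 = 32.4, so m is about 2.

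**4. What the table would change.** It changes nothing in step 2. Those probabilities describe the cost of an imperfect reference standard, which the plan accepts, and they define accuracy against the true state, whereas section 11.3 defines it against TRUS.

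**5. How much the table could show.** The men concerned number 5 under the plan's alternative and 18 under its null. 90% intervals for the share confirmed on targeted cores:

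| Confirmed | 90% CI |
|---|---|
| 0/5 | 0% to 45% |
| 2/5 | 8% to 81% |
| 5/5 | 55% to 100% |
| 7/12 | 32% to 82% |
| 9/18 | 29% to 71% |

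**6. Limits beyond sample size.** Only MRI-reclassified men get targeted cores, so the information can only favour the MRI. Section 5.3.3 leaves technique to the institution and core number to the physician, so a negative targeted biopsy may itself be a miss. The extent rules differ in units (over 7 mm on targeted cores, over 50% of a core on TRUS). The TRUS criterion of more than 3 positive cores has no targeted equivalent.

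**The case for a change.** The strongest reply is that pre-specification is cheap here and carries weight. The protocol hopes MRI might replace repeat biopsy (section 2.1), so the make-up of the false positives matters. At 12/90, moving a single man to the true positives would bring the upper limit below 20%. A table named in advance is more persuasive than one added after a failure, and it needs no new data.

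Part of this stands. Section 11.6 does not commit to the split, and a report that includes it, with its one-way bias stated, would be more informative. But the example at 12/90 is a reason for caution: with verification confined to MRI-positive men, an adjusted FPF could only move towards success. The TRUS-based rule protects against that, and the objection does not ask for the rule to change. What remains is a preference for naming one descriptive table.

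**Conclusion.** No change follows. This is a gap that analysts fill sensibly. The stated secondary objective is analysed, the wording of section 11.6 accommodates a breakdown by TRUS result, and the source-labelled cores supply the data. No test, error rate, sample size or decision rule depends on it, and the stated power reproduces (0.818 against 81%).

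The fall from 99% to 41% in the chance of meeting the FPF criterion depends on an assumed eight TRUS misses and a 90% flag rate among the missed men. With about two misses, as the rebiopsy series suggests by the same subtraction, it is 97%. In either case it measures the accepted reference standard, not the missing table. With 5 to 18 men and one-directional verification, the table could illustrate discordant cases but could not reliably separate TRUS misses from MRI over-calls.
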